- **Methods, Research Plan, and Design**

- **Study design**

This study will be a prospective 2-year randomized, open label, clinical trial, using daily dose sublingual versus twice daily dose sublingual versus transdermal 17-beta estradiol in transgender female patients. Primary outcome is degree of testosterone suppression. Secondary outcome to measure safety and tolerability will

include liver enzymes, thrombogenic, and metabolic factors. Patients will be evaluated every 6 months during the length of the study

b. Subjects

Inclusion criteria: Female transgender patients between the ages of 18 to 45 years of age who are seen at the Washington University Transgender Center. Patients must have met the eligibility and readiness criteria for gender-affirming hormone therapy.

Exclusion criteria: Use of GnRH agonist for the last 12 months, history of liver disease, dyslipidemia requiring treatment, drug use, alcohol use (>2drinks per day), cigarette smoking, history of blood clot (venous thromboembolism, pulmonary embolism), history of hyperkalemia, history of Addison's disease, concomitant use of eplerenone.

Patients who have been referred to the Washington University Transgender Center for feminizing hormonal therapy and meet the inclusion criteria, will undergo consent process before initial evaluation. Methods for recruitment includes phone calls, emails, letters, and EPIC slicer dicer. For consent, physical or electronic consent form will be provided.

If consent is obtained, patients will be assigned to either daily sublingual vs twice daily sublingual vs transdermal 17-beta estradiol. Assignment will be done through block randomization.. Using the inclusion criteria, our center provides care to 150-200 new transgender female patients in a year for initiation of female hormone therapy.

We aim to enroll a total of 70 patients. This is a pilot study, which results will guide the feasibility, design, and implementation of a larger clinical trial. To account for 15% of potential dropout, we have planned to enroll a total of 80 patients.

- Research Plan**

The proposed clinical trial involves 2 research aims to be conducted over two years (Table 1). Subjects will be recruited from the Washington University Transgender Center. The Center is projected to see more than 1,000 patients every year, of which 150-200 are new transgender female patients for initiation of FHT.

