Patients who agree to participate in the study and meet inclusion criteria will undergo the evaluation described in Table 2. Data of interest will be collected on all patients enrolled and will be saved on a database created in Research Electronic Data Capture (REDCap). Information to be collected will include:

1. Demographic and anthropometric variables: Parameters will be routinely collected through chart review.
2. Laboratory testing: During each visit, we will obtain hormone levels, coagulation factors, metabolic factors, electrolytes level. A hematologist will review the lab results and communicate any recommended interventions (including stopping medication) to the participant's treatment team.

Initial evaluation will include patient history, physical examination, and baseline labs. During the initial visit, patients will be started on spironolactone and 17-beta estradiol transdermal or or daily sublingual or twice daily sublingual based on their treatment group assignment. Our team will check hormonal levels every 4 weeks (+/- 2 weeks) until estradiol level is within goal (see dosing guidelines) as established by standard of care. Once patients are started on estradiol, they will be asked to attend 6 more visits for the 2 years duration of the study as described in table 2.

Dosing guidelines:

Per the current standard of treatment, all study medications are initiated at the lowest available clinical dose and titrated to effectiveness at the study clinician's discretion by 6 months of study participation, using plasma total testosterone level in the cisgender female range (<50ng/dL) with serum estradiol level that should not excess the peak physiologic range 100-200 pg/mL. In some cases, medication doses will be titrated at monthly study follow up visits to optimize treatment response.

Spironolactone:

Starting dose will be 50 mg daily

Plan to increase 50 mg monthly to standard dose of 200 mg daily

For patients randomized to transdermal (patch) estradiol:

Starting dose will be 100 mcg/24hrs

Plan to increase by 100 mcg/24hrs every month

Max dose 400 mcg/24hrs

Goal is to achieve a serum estradiol level between 100-200 pg/mL and to suppress testosterone to cisgender female levels

Estradiol levels will be measured in the morning (fasting sample)

For patients randomized to daily sublingual estradiol:

Starting dose will be 2 mg daily

Plan to increase every month by 2 mg daily

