Baseline characteristics and laboratory results will be reported as mean \pm SD, median (interquartile range), or percentages. Independent T-test will be used to analyze the difference between treatment groups. We may use Wilcoxon rank sum test in case of non-normal distribution.

g. Limitations and contingent plans

A potential limitation to this study is the difficulty of recruitment since the PI is a First Year Clinical Fellow with a heavy clinical rotation. Our project is also supported by the director of the Washington University Transgender Center which will improve the recruitment of patients. Also, the co-directors of the Washington University Transgender Center at St Louis Children's Hospital are supporting the project, therefore, we could increase our enrollment numbers by recruitment patients seen in their clinic. Another limitation is the cost of the entire panel of thrombogenic factors. We could address this by just testing the most valuable test (thrombin) which has been used in previous research to assess the thrombotic risk in postmenopausal women on hormone replacement therapy.

- **References**

- Unger CA. Hormone therapy for transgender patients. *Transl Androl Urol.* 2016;5(6):877-884. doi:10.21037/tau.2016.09.04
- American Psychiatric Association. Diagnostic and Statistical Manual of Mental Disorders. 5th ed. Washington, DC: American Psychiatric Press; 2013
- Unger CA. Hormone therapy for transgender patients. *Transl Androl Urol.* 2016;5(6):877-884. doi:10.21037/tau.2016.09.04
- Unger CA. Hormone therapy for transgender patients. *Transl Androl Urol.* 2016;5(6):877-884. doi:10.21037/tau.2016.09.04

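### Medication may be stopped on the same laboratory results that are the Aim 2 outcomes, and the plan does not say how stopped patients enter the Aim 2 comparison

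*Combined protocol and SAP*

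**What the plan says.** Under Study design, the secondary outcomes for safety and tolerability "include liver enzymes, thrombogenic, and metabolic factors". Under Research Plan, item 2 (Laboratory testing), hormone, coagulation, metabolic and electrolyte results are obtained at each visit, and a hematologist reviews them and will "communicate any recommended interventions (including stopping medication", to the treatment team. No threshold or expected frequency is given. The same section states that "Data of interest will be collected on all patients enrolled".

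Hypothesis 2a expects more estrone on sublingual estradiol and, through it, raised thrombogenic factors. For metabolic factors it predicts change without a direction.

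Loss of patients is mentioned once, under Subjects: "We aim to enroll a total of 70 patients", and then "To account for 15% of potential dropout, we have planned to enroll a total of 80 patients". The comparative analysis, under Statistical methods and Data Analysis, is "Independent T-test will be used to analyze the difference between treatment groups", with a Wilcoxon rank sum test if the data are not normal. No analysis visit, analysis set, missing-data rule or rule for values after a stop is given, and stops are not listed as an outcome.

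**The concern.** The measurements that can prompt a stop are the measurements to be compared. If sublingual estradiol raises thrombogenic factors, more sublingual than transdermal patients will have results that could lead to a recommended stop, and they will tend to be those with the highest values. What happens to their later values then affects the arm difference.

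A t-test or Wilcoxon test at a later visit has two options. It can leave out stopped patients who have no value at that visit, which removes high values mainly from the sublingual group. Or it can include values taken off drug, which may no longer carry the drug effect. Enrolling extra patients restores numbers but does not correct selection.

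The trial is a pilot meant to guide a larger one, so an understated safety difference would carry forward. The stops themselves bear directly on safety and tolerability, yet the plan does not ask for them by arm.

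**Working it through.** **The plan's own figure.** 70 × 1.15 = 80.5, which matches the stated 80. (Dividing instead gives 70 / 0.85 = 82.4, and 80 × 0.85 = 68.) The 15% is total dropout and is not tied to laboratory stops. It is used below only as a ceiling on plausible losses.

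**Assumptions, none of them in the documents.** Equal allocation to the three arms, with the two sublingual arms pooled (53 sublingual, 27 transdermal); values with SD 1 and a true difference of 0.6 SD at every post-baseline visit; correlation 0.7 between visits; four post-baseline visits (6, 12, 18 and 24 months, as in Table 2); every patient above a threshold at any of the first three visits is stopped and has no later values. 4,000 simulated trials per setting.

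**Case A: stopped patients are lost.** Patients lost = 53 × sublingual share + 27 × transdermal share. Understatement = 1 − observed difference / 0.60.

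| Threshold | Stopped, sublingual vs transdermal | Lost of 80 | Month-24 difference | Understatement |
|---|---|---|---|---|
| +1.5 SD | 32% vs 13% | 17.0 + 3.5 = 20.5 (26%) | 0.40 | 33% |
| +2.0 SD | 16% vs 5% | 8.5 + 1.4 = 9.9 (12%) | 0.47 | 22% |
| +2.5 SD | 6% vs 1.5% | 3.2 + 0.4 = 3.6 (4.5%) | 0.53 | 12% |

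The first row loses more than the planned 15% to laboratory stops alone, so only the other two rows are compatible with the plan: 12% to 22%. At month 6 the difference is 0.60 in every row, because nobody has yet been stopped.

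**Cross-check by formula.** With true difference δ, a common cut-off c and correlation ρ between the triggering value and the analysed value, the difference among those who remain is δ − ρ[λ(δ) − λ(0)], where λ(μ) = φ(c − μ) / Φ(c − μ). Choose c so that a share s of all patients is lost: (2/3)[1 − Φ(c − δ)] + (1/3)[1 − Φ(c)] = s. For δ = 0.5, ρ = 0.7 and s = 15%, the losses are 18.4% and 8.1%, c is about 1.40, λ(0.5) = 0.326 and λ(0) = 0.163. The result is 0.5 − 0.7 × 0.163 = 0.39, a 23% understatement. Over δ from 0.5 to 0.8, ρ from 0.3 to 1.0 and s from 2.5% to 15%, the understatement runs from 3% to 33%. At ρ = 0 it is zero.

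**Case B: stopped patients are kept, and off-drug values are analysed with the rest.** Assume further that the excess sublingual effect vanishes off drug. The month-24 difference is then about 0.6 × (1 − sublingual share stopped): 0.6 × 0.68 = 0.41, 0.6 × 0.84 = 0.50 and 0.6 × 0.94 = 0.56. Simulation gives 0.41, 0.51 and 0.56. Retention alone therefore leaves most of the attenuation in place.

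**Case C: use all values up to and including the triggering one.** Sequential regression on those values, which serves the same purpose as a repeated-measures model, recovers 0.59 to 0.60 at all three thresholds. It works because the value that led to the stop is in the data. A single-visit test at month 24 ignores it.

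**The case against.** A reader might infer that the plan tests only the patients who remain, so that those with the worst values are removed from the safety comparison. The documents do not say this. No completer or available-case set is named, and data collection is said to cover all enrolled patients. Stopping medication is not the same as leaving the study. The hematologist advises the treatment team and does not stop treatment directly. The abnormal value is recorded when it prompts the recommendation, so only later values are at risk, and the plan names no analysis visit. All of this stands.

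It is also fair that the size is set by assumptions: threshold, effect, correlation, pooling of the sublingual arms and complete loss after a stop. If stops are rare or Hypothesis 2a is wrong, there is little or no bias in the arm difference. The +1.5 SD setting cannot serve as an upper bound, since it exceeds the plan's own dropout allowance.

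Finally, following and analysing everyone as randomised does not by itself restore the difference expected had nobody stopped (Case B). That objection is right about retention alone, and it is why off-drug values need a stated rule.

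What it does not remove is the gap. Collecting data on everyone enrolled does not say whether visits continue after a stop, or how the values enter a two-sample test. The link between trigger and outcome makes this more specific than a generic missing-data omission.

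**Conclusion.** The concern holds in a conditional form. The plan permits stopping that depends on the Aim 2 outcomes and, under its own hypothesis, on the arm, and its only stated test has no rule for the patients concerned. Bias toward no difference in the later-visit thrombogenic comparison cannot be excluded, but the documents do not show that it will occur.

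Under the assumptions above, with losses within 15%, the month-24 difference of 0.6 SD would be understated by about 12% to 22% if stopped patients are lost. It would be understated by about 6% to 16% if they are kept, off-drug values are pooled in and the excess effect vanishes off drug (1 − 0.56/0.60 = 7% and 1 − 0.51/0.60 = 15% from the rounded simulation results). The direction rests on Hypothesis 2a and applies to thrombogenic factors; no direction is stated for metabolic factors. The stronger conclusion, that the plan excludes the worst-affected patients, is not supported. This is worth correcting because the remedy is cheap, although it concerns a secondary outcome of a pilot.

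**What to change.** In Statistical methods and Data Analysis:

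- Analyse all randomised patients in their assigned arm.
- For the Aim 2 laboratory outcomes, replace the single-visit t-test with one repeated-measures model (arm, visit, arm by visit, baseline value), using all values up to and including the visit that led to a stop. State that it estimates the difference had medication continued, and that it assumes stops are explained by recorded values.
- Continue the Table 2 laboratory visits after a stop, flag those values as off drug, and include them in a separate as-randomised (treatment-policy) analysis.
- Report recommended and actual stops by arm, with reason and exact confidence intervals, as an Aim 2 safety and tolerability outcome.

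The cost is analysis text, a recorded date and reason for each stop, some effort to retain patients who have stopped, and a little more analysis. The laboratory visits are already scheduled. No stopping rule is proposed.

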Goal is to achieve serum estradiol level between 100-200 pg/mL and to suppress testosterone to cisgender female levels.

Estradiol levels will be measured in the morning (fasting sample).

For patients randomized to twice daily dose sublingual estradiol

Starting dose will be 1 mg twice daily

Plan to increase every month by 2 mg daily

Goal is to achieve serum estradiol level between 100-200 pg/mL and to suppress testosterone to cisgender female levels

Estradiol levels will be measured in the morning (fasting sample).

Table 1. Planned Research Timeline

Data cleaning and analysis										•	•	•	•
Grant application				•	•	•	•						
Final results manuscript										•	•	•	
Presentation preparation										•	•	•	

Table 2. Description of the evaluation and laboratory testing in each visit during the clinical trial

Study visit	Baseline	6 months +/- 2 months	12 months +/- 2 months	18 months +/- 2 months	24 months +/- 2 months
Anthropometric measurement	•	•	•	•	•
Metabolic factors	•	•	•	•	•
Hormone levels	•	•	•	•	•
Electrolytes	•	•	•	•	•
Liver function test	•	•	•	•	•
Coagulation factors	•	•	•	•	•
Lipid Panel	•		•		•

- Benefit/Risk assessment**

i. Benefits

Direct benefits from this study to participants are anticipated. During the research study, their tolerability and side effects will be monitored closely so any changes can be detected earlier. Also, participants may feel gratified by contributing to the field. Patients will have the opportunity to help us improve services and treatment options for them and future generations.

ii. Risks

Potential risks with this study are no different than the risks that may occur while receiving gender affirming therapy. This may include changes in their lipoprotein profile and triglycerides level (14) and increase risk of venous thromboembolism, diabetes, high blood pressure, coronary heart disease, hepatotoxicity. While the patient is receiving gender affirming therapy, the investigators will provide careful attention to laboratory results.

Laboratory testing will be obtained every 3 months for the first year, and every 6 months on the second year. For this purpose, placement of an intravenous (IV) access may be required. IV access or venipuncture may be associated with possible minor discomfort or pain when inserted.

- Statistical methods and Data Analysis**

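### The Research Plan promises six post-baseline visits as in Table 2, but Table 2 lists four; the month 3 and month 9 laboratory tests are missing, and electrolyte testing during spironolactone titration is left unclear

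*Combined protocol and SAP*

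**What the plan says.** Four places in the combined protocol and SAP bear on the visit schedule.

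- **Study design:** "Patients will be evaluated every 6 months during the length of the study".
- **Research Plan:** once estradiol is started, "they will be asked to attend 6 more visits for the 2 years duration of the study as described in table 2".
- **Table 2**, titled "Description of the evaluation and laboratory testing in each visit during the clinical trial": columns for baseline and months 6, 12, 18 and 24, each post-baseline column with a window of 2 months either side. Electrolytes, hormone levels, metabolic factors, liver function and coagulation factors are marked in every column.
- **Risks**, under Benefit/Risk assessment: "Laboratory testing will be obtained every 3 months for the first year, and every 6 months on the second year".

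Three further statements decide when electrolytes might be measured. The laboratory item in the Research Plan reads "During each visit, we will obtain hormone levels, coagulation factors, metabolic factors, electrolytes level". Early monitoring is described as "Our team will check hormonal levels every 4 weeks (+/- 2 weeks) until estradiol level is within goal". The Dosing guidelines add: "In some cases, medication doses will be titrated at monthly study follow up visits to optimize treatment response".

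Spironolactone starts at 50 mg daily and is planned to rise by 50 mg each month to 200 mg. Titration of all study drugs is left to the study clinician's "discretion by 6 months of study participation".

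**The concern.** Staff usually work from the assessment table, and the Research Plan sends them to it. If they follow Table 2, two rounds of laboratory testing that the Risks text promises will not take place.

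Two consequences follow. First, thrombogenic and metabolic factors are named safety outcomes, and their number of year 1 measurements depends on which schedule is used. Second, the trial excludes people with a history of hyperkalemia, and a hematologist is to review laboratory results and may recommend stopping medication. On Table 2 alone, there would be no tabulated post-baseline electrolyte result to review while spironolactone is raised from 50 mg to 200 mg.

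**Working it through.** **1. The plan's own figure.** The Research Plan states 6 post-baseline visits. The Risks frequency gives 12/3 = 4 time points in year 1 (months 3, 6, 9, 12) and 12/6 = 2 in year 2 (months 18, 24). The total is 4 + 2 = 6, so these two places agree.

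**2. The other count.** Table 2 has post-baseline columns at months 6, 12, 18 and 24, which is 4. Study design gives 24/6 = 4. Counting the baseline column would give 5, still not 6.

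**3. The difference.** {3, 6, 9, 12, 18, 24} less {6, 12, 18, 24} leaves months 3 and 9. The Table 2 windows are months 4-8, 10-14, 16-20 and 22-26. Neither month 3 nor month 9 lies in any of them, so the windows do not reconcile the two schedules.

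**4. Year 1 measurements.** Under Table 2, coagulation and metabolic factors have 2 post-baseline points (months 6 and 12). If the Risks frequency is combined with the Research Plan's list of tests for each visit, they have 4. That list does not mention liver enzymes, so their number under the Risks text is unknown.

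**5. Electrolytes against spironolactone.** The planned doses are 50, 100, 150 and 200 mg at months 0, 1, 2 and 3 (50 + 3 x 50 = 200). The first post-baseline electrolytes in Table 2 fall at 6 - 2 = 4 to 6 + 2 = 8 months. On the planned pace, a participant has then been on 200 mg for 4 - 3 = 1 to 8 - 3 = 5 months.

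The table below counts how many of the three increases come strictly before the first electrolyte result. The slow pace is an assumption: titration stretched evenly to the 6-month limit, with steps at months 2, 4 and 6.

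| First electrolytes taken at | Planned pace (months 1, 2, 3) | Slow pace (months 2, 4, 6) |
|---|---|---|
| Table 2 alone, months 4-8 | 3 of 3 | 1 to 3 of 3 |
| Month 3 test, +/- 2 weeks | 2 or 3 of 3 | 1 of 3 |
| First 4-weekly draw, weeks 2-6 | 0 or 1 of 3 | 0 of 3 |

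On the slow pace under Table 2 alone, time on 200 mg before the first result is 0 to 8 - 6 = 2 months.

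**The case against.** The strongest reply is that the electrolyte gap exists only if Table 2 is read by itself. The Research Plan lists electrolytes among the tests at each visit and the Dosing guidelines mention monthly follow-up visits, so month 3 and some titration visits may already be covered. Titration is also at the clinician's discretion, so 200 mg at month 3 is a plan and not a fixed exposure. This stands as a limit on the size of the gap. It does not close it. The monthly visits apply only in some cases, the text does not say that they count as visits for the list of tests, and the Risks sentence names no analytes. The 4-weekly checks name hormone levels only and stop when estradiol reaches goal, which need not coincide with the end of spironolactone titration.

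A second reply is that the Risks sentence gives a laboratory frequency, not a number of visits, and that it introduces the discomfort of venipuncture. That is correct: only the Research Plan states six visits, and the six from the Risks text is derived. The conflict survives without it, because the Research Plan misdescribes the table that it cites.

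A third reply is that two places support each schedule, so Table 2 may be the one intended. The documents do not settle this, and the fix has to allow for either.

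Damage in the text extraction is an unlikely explanation. Table 2 has five complete columns with aligned rows, and Study design gives the 6-monthly schedule independently.

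**Conclusion.** The inconsistency is certain: six post-baseline visits in the Research Plan, matched by the six time points of the Risks text, against four in Table 2 and Study design. Following Table 2 loses the month 3 and month 9 laboratory tests.

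The electrolyte point is conditional. On Table 2 alone and on the planned pace, all three spironolactone increases precede the first tabulated post-baseline result, with 1 to 5 months already spent on 200 mg. The gap is smaller if titration is slower, or if the month 3 test or the monthly titration visits include electrolytes.

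A reader might infer more than this, and the documents do not support it:

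- **That participants will go without potassium monitoring during titration.** The text leaves this open.
- **That hyperkalemia events will be missed.** The documents give neither a hyperkalemia rate nor a required testing interval, so no count can be made.
- **That the comparison of arms is biased.** All arms share one spironolactone schedule.
- **That the primary outcome is lost.** Hormone levels are marked at every Table 2 visit, including month 24.

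This should be corrected because it concerns safety monitoring and the correction is cheap.

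**What to change.** **1. Make Study design, the Research Plan, the Risks text and Table 2 agree.** Preferably, add month 3 and month 9 safety laboratory columns to Table 2 with at least electrolytes, metabolic factors and hormone levels. Use a window under 1 month so that they do not overlap months 4-8 and 10-14. Correct Study design to 3-monthly in year 1 and 6-monthly in year 2. This keeps the Risks promise and the Research Plan's count. If the 6-monthly schedule was intended, correct the six visits in the Research Plan and the 3-monthly frequency in Risks instead.

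The preferred version costs two more laboratory visits per participant than Table 2 shows: 2 x 80 = 160. If the planned 15% drop out before month 3, it is 2 x (80 x 0.85) = 2 x 68 = 136. Coagulation factors and liver tests at these two visits are the investigator's choice. Coagulation would add up to 2 x 80 = 160 tests, and the limitations section already names the cost of the thrombogenic panel as a constraint.

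**2. Under either schedule, run electrolytes on the 4-weekly hormone draws while spironolactone is being increased.** Continue until a result is available after the last increase, even if estradiol reaches goal earlier. Say also whether monthly titration visits carry the full list of tests. A footnote to Table 2 is enough.

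Most of this uses blood already drawn. Assume the planned pace, exact 4-week spacing, the last increase at week 12, full attendance and the month 3 visit in place. The added electrolyte tests then fall at weeks 4, 8 and 16, which is 3 per participant, or 3 x 80 = 240. A participant at estradiol goal by week 4 would need 2 draws not otherwise planned (weeks 8 and 16); one still above or below goal through week 16 would need none. If the 6-monthly schedule is kept, week 12 is added to both counts, giving 4 tests and up to 3 extra draws. Slower titration lengthens the series, and the +/- 2 week window can add or remove a draw.

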Study Protocol Cover page

Title: Effectiveness, safety, and tolerability of different estradiol dosing regimens in transgender females.

NCT Number: NCT05010707

Date: May 26, 2022

Washington University in St. Louis

Version Date: May 26th, 2022

Principal Investigator: [name]

Study Title: Effectiveness, safety, and tolerability of different estradiol dosing regimens in transgender females.

Faculty Sponsor: [name]

- **Objectives**

The purpose of this open label, pilot, randomized clinical trial is to evaluate the effectiveness, safety and tolerability of estrogen use in transgender female and the degree of testosterone suppression achieved in this population when placed on sublingual 17-beta estradiol in comparison to transdermal 17-beta estradiol for gender affirming pharmacological therapy over the first two-years of treatment.

This study is important because, to our knowledge, this is the first randomized clinical trial evaluating the effectiveness, safety, and tolerability of estrogen in transgender female. There are no previous data comparing the different presentation of estrogen options in transgender women; therefore, this clinical trial will determine the best strategies and methods required to develop a larger randomized clinical trial. This study will also provide information useful to close the medical knowledge gap to provide safe and competent care to transgender female patients.

Aims

Aim 1. In this randomized clinical trial, we will evaluate the degree of testosterone suppression by measuring total testosterone level in transgender female patients undergoing hormonal affirming therapy randomized to sublingual 17 beta estradiol or transdermal 17 beta estradiol, in conjunction with spironolactone (antiandrogen), for a period of 2 years.

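### Three arms are randomised, but the aims describe two groups and the statistics section plans only two-sample tests, so the primary comparison (which arms, pooled or not, at which visit) is undefined

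*Combined protocol and SAP*

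**What the plan says.** The Study design section describes an open-label trial "using daily dose sublingual versus twice daily dose sublingual versus transdermal 17-beta estradiol in transgender female patients", and the Subjects section assigns patients to those three arms by block randomisation. Aims 1 and 2 each name two groups, sublingual or transdermal.

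On the outcome, Study design says "Primary outcome is degree of testosterone suppression", and Aim 1 adds that "we will evaluate the degree of testosterone suppression by measuring total testosterone level in transgender female patients". Study design also says "Patients will be evaluated every 6 months during the length of the study", and Table 2 schedules hormone levels at baseline and at months 6, 12, 18 and 24.

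The section Statistical methods and Data Analysis has three sentences. One lists descriptive summaries. The other two are "Independent T-test will be used to analyze the difference between treatment groups" and "We may use Wilcoxon rank sum test in case of non-normal distribution". No section gives a significance level, a multiplicity rule, a pooling rule or a primary visit.

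On size and purpose, the Subjects section says "We aim to enroll a total of 70 patients", plans 80 enrolled to allow for 15% dropout, and states "This is a pilot study, which results will guide the feasibility, design, and implementation of a larger clinical trial".

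**The concern.** A t-test and a rank sum test each compare two samples. With three arms, neither defines an analysis until someone says which groups enter it. The documents support three readings:

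- **Twice-daily sublingual v transdermal.** Hypothesis 1a expects more suppression with several sublingual doses a day. Its hypothesis sentence names no comparator; transdermal appears only in the rationale that follows.
- **Pooled sublingual v transdermal.** Aim 1 and Hypothesis 2a treat sublingual as one group.
- **A three-way comparison.** Study design sets all three regimens against each other.

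The statistics section adopts none of these, and no hypothesis gives the once-daily arm a role of its own. The visit is also open, and so is the form of the outcome: a level, a change from baseline, or the share of patients below the 50 ng/dL level in the Dosing guidelines.

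Arms, pooling and visit could therefore all be settled once results are known. A chance difference, or a real one diluted by pooling, could then be carried into the design of the larger trial.

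**Working it through.** **Inputs from the documents.** Three arms; 70 patients targeted; 80 enrolled; 15% dropout; four visits after baseline (Table 2).

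**Assumptions not in the documents.** Two-sided 0.05 per test, 1:1:1 allocation, normal data, equal variances, no true difference between arms.

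**The plan's own figure.** 70 × 1.15 = 80.5, which agrees with 80 (dividing instead, 70/0.85 = 82.4). The 70 cannot be reproduced, because no power, effect size or standard deviation is given.

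**Patients per arm.** 70/3 = 23.3; 80 × 0.85 = 68 and 68/3 = 22.7. I use 23, so a three-arm model has 69 − 3 = 66 degrees of freedom.

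**Chance of at least one false positive**

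1. One prespecified contrast at one visit: 5% (simulated 0.049-0.050).
2. Three pairwise t-tests at one visit. With a common variance this is P(Q > √2 × t), where Q is the studentised range for 3 groups and 66 df, and t = 1.997 is the two-sided 5% critical value. √2 × 1.997 = 2.824, and the probability is 0.121. Simulation of separate t-tests gives 0.120-0.122. With 22 or 26 per arm it is 0.121 or 0.124.
3. The smaller p-value of twice-daily v transdermal and pooled v transdermal. Take the variance of one arm mean as 1. The two differences have variances 1 + 1 = 2 and 1/2 + 1 = 1.5 and covariance 1/2 + 1 = 1.5, so their correlation is 1.5/√(2 × 1.5) = 0.866. That much overlap keeps the inflation modest: simulated 0.071-0.075.
4. One contrast with the visit picked afterwards from four (simulated):

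| Between-visit correlation | 0.3 | 0.5 | 0.7 | 0.9 |
|---|---|---|---|---|
| Chance of a false positive | 0.176 | 0.158 | 0.132 | 0.093 |

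**Why the contrast matters for power.** Detectable differences at 80% power come from the noncentral t distribution with 66 df and noncentrality d/√(1/n₁ + 1/n₂), before any gain from a covariate.

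- 23 v 23 at 0.05: √(1/23 + 1/23) = 0.295, detectable d = 0.838 SD.
- 46 v 23 at 0.05: √(1/46 + 1/23) = 0.255, detectable d = 0.726 SD.
- 23 v 23 at 0.05/3 (Bonferroni over three pairs): 0.975 SD.
- Three-arm F-test, then pairwise tests only if it is significant (simulated): 0.88 SD if the third arm equals one of the pair, 0.94 SD if it lies midway.

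Suppose twice-daily differs from transdermal by 0.838 SD and the sublingual arms are pooled. If once-daily has the same effect, the pooled difference is 0.838 SD, noncentrality 0.838/0.255 = 3.28, power 90%. If once-daily equals transdermal, the pooled difference is 0.838/2 = 0.419 SD, noncentrality 0.419/0.255 = 1.64, power 37%.

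**Level or change.** Write Y for testosterone at the visit, B for baseline and T for the treatment terms. If Y = a + bB + T, then Y − B = a + (b − 1)B + T. Only the baseline coefficient moves. With baseline as covariate and the same scale, the treatment contrast is identical.

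**The case against.** The strongest reply is that this is a pilot. It claims no power, significance level or error rate, and the Innovation section describes its output as preliminary data. A reader might infer that the plan breaks a type I error guarantee, or that the trial's real error rate is 12%, or as high as 22-38% if every pair were tested at all four visits (correlation 0.9 to 0.3). The documents do not support that. There is no stated rate to breach, every percentage above rests on an assumed 0.05, and no section says that all twelve tests would be run or that any one positive would count as success. This part of the reply stands: the defect is an undefined comparison, and the percentages only illustrate what the freedom of choice could cost.

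A second reply is that Hypothesis 1a and the two-year period in Aim 1 already imply twice-daily v transdermal at month 24. They hint at it, but neither is declared primary or carried into the statistics section. Aim 1's wording points to pooling, and month 6 also has support, because the Dosing guidelines expect titration to be complete by then.

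Pilot status does not remove the point. The plan names a primary outcome and a directional hypothesis, plans tests without calling them exploratory, and will use the results to design a larger trial.

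**Conclusion.** The concern holds as a gap in specification. Two-sample tests are planned for a three-arm trial, and the arms compared, the pooling of the sublingual arms and the visit are all open. Under the assumptions listed in the working, choosing among the readings afterwards raises the chance of a false positive from 5% to 7-8% (twice-daily or pooled contrast), 9-18% (visit) or about 12% (three pairs at one visit). The choice of contrast also decides whether a 0.84 SD twice-daily effect is sought with about 80% power or, if pooled with an ineffective once-daily arm, with 37%. The trial's actual type I error cannot be calculated. It should be fixed, but as a pilot the trial is not invalidated by it.

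**What to change.** Rewrite Aims 1 and 2 for three arms. In the statistics section, replace the separate two-sample tests of the primary outcome with one three-arm linear model of total testosterone at one named visit, with baseline testosterone as covariate. Fix the scale (for example log) in advance, keep a rank-based sensitivity analysis for skewed values, and report the proportion below 50 ng/dL as a secondary summary.

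Name the visit. Month 24 fits Aim 1's period; month 6 fits the titration period. All arms are titrated towards the same testosterone and estradiol goals, so state how that affects interpretation.

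Clinicians see these levels in an open-label trial, so the commitment should be made before any between-arm comparison. Choose one, using two-sided 0.05 where a test is made:

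- (a) twice-daily sublingual v transdermal as the single primary contrast;
- (b) pooled sublingual v transdermal as the single primary contrast;
- (c) an overall three-arm F-test, with pairwise tests only if it is significant;
- (d) all contrasts as estimates with 95% confidence intervals, labelled exploratory, which suits a pilot.

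Report remaining contrasts, other visits and the Aim 2 outcomes as exploratory. In simulation with an assumed baseline correlation of 0.5, (a) and (b) have error 0.048. Option (c) has 0.048 with no differences, and 0.045-0.051 for the null pair when one arm differs.

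**Cost.** A few sentences, no extra patients or samples. Under (a) and (b) the other contrasts cannot be claimed as confirmatory. Option (b) loses power if once-daily resembles transdermal. Option (c) needs 0.88-0.94 SD rather than 0.84 SD at 80% power. Option (d) gives up a confirmatory claim.

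Separately, the visit and laboratory schedules must be reconciled. Study design and Table 2 give four visits after baseline; the Research Plan gives six while citing Table 2; the laboratory schedule under Risks also gives six (four in year one, two in year two).
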